9 All vital signs measurements are to be obtained in the sitting position following at least 5 minutes of rest. All measurements will be taken in triplicate, approximately 2 minutes apart. When possible, blood pressure (BP) should be taken in the non-dominant arm throughout the trial, using the same methodology (automated or manual) and ensuring that an appropriately sized cuff is used. For virtual visits, patients will be instructed on the proper use of and will be provided with WiFi/Bluetooth connected devices for measuring and transmitting data on blood pressure, and temperature during virtual trial visits. The data are stored and automatically transferred when connected to WiFi.

10 A single 12-lead ECG will be performed in the supine position following a period of at least 10 minutes of rest.

11 A urine pregnancy test may be performed to expedite availability of results prior to dosing on Day 1. Except for virtual visits, all other pregnancy tests will be serum tests; dosing may continue with results pending. At sites where pregnancy tests are required for virtual visits, at Visit 1 women of child-bearing potential will be given urine pregnancy kits for use at each of the virtual visits.

[REDACTED]

14 Assessments will only be performed at Study Weeks 4, 8, and 12.

[REDACTED]

16 The Baseline/Screening version of the scale is the initial form of the instrument to assess suicidality in a patient's lifetime and is administered at Screening. In order to be eligible for the trial, a patient at Screening cannot have a suicidal ideation of type 4 or 5, a suicide attempt during the patient's lifetime, or any suicidal behavior in the last month, as per the C-SSRS. After Screening, the 'Since Last Visit' version of the scale will be used to assess suicidality since the patient's last visit. If at any time during the trial a patient has a suicidal ideation of type 4 or 5, or any suicidal behavior, the patient should be referred to a mental health professional (MHP).

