6.2. Patient Exclusion Criteria

Patients meeting any of the following criteria are not eligible for trial participation:

1. Patients with the following genetic variants: biallelic Bardet-Biedl Syndrome (BBS); biallelic Alström Syndrome 1 (ALMS1); homozygous, heterozygous, or compound heterozygous variants in MC4R, POMC, PCSK1, LEPR, nuclear receptor coactivator 1 (NCOA1; steroid receptor coactivator-1 [SRC1]) or SRC homology 2 B adapter protein 1 (SH2B1) genes as well as 16p11.2 chromosomal deletions that include the SH2B1 gene.
2. Weight loss >2% in the previous 3 months.

Patients will not be excluded for using regimens for weight maintenance or to prevent weight gain, such as dietary and/or exercise regimens, or medications, supplements or herbal treatments (e.g., orlistat, lorcaserin, phentermine, topiramate, naltrexone, bupropion, glucagon-like peptide-1 [GLP-1] receptor agonists, etc.), provided:

- the regimen and/or dose has been stable for at least 3 months prior to randomization

- the patient has not experienced weight loss >2% during the previous 3 months, AND
 - the patient intends to keep the regimen and/or dose stable throughout the course of the trial.
3. Bariatric surgery or procedure (e.g., gastric bypass/band/sleeve, duodenal switch, gastric balloon, intestinal barrier, etc.) within the last 6 months. All patients with a history of bariatric surgery or procedures must be discussed with, and receive approval from, the Sponsor prior to enrollment.
 4. Documented diagnosis of current unstable major psychiatric disorder(s) (e.g., major depressive disorder, bipolar disorder, schizophrenia, etc.) or documented worsening psychiatric condition that required changes in treatment regimen within the previous 2 years, or other psychiatric related risks that the Investigator believes may interfere with trial compliance or patient safety.
 5. Clinically significant depression or suicidality, as defined by: any suicidal ideation of type 4 or 5 on the Columbia-Suicide Severity Rating Scale (C-SSRS) during Screening, any suicide attempt during the patient's lifetime, any suicidal behavior in the last month, or a Patient Health Questionnaire-9 (PHQ-9) score of ≥ 15 during Screening process.

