8.9.9. Suicidal Ideation and Depression Monitoring

As setmelanotide is considered to act through the central nervous system (CNS), suicidal ideation and risk will be assessed using the C-SSRS scale (Section 8.9.9.1) and depression will be assessed using the PHQ-9 or the Children's Depressive Inventory-2 (CDI-2) (Section 8.9.9.2 and 8.9.9.3).

A patient should be referred to a mental health professional (MHP) if he/she has:

- Any suicidal behavior
- Any suicidal ideation of type 4 or 5 on the C-SSRS
- A PHQ-9 score of ≥ 10
- A CDI-2 score of > 20

A referral to a MHP should also be made if in the opinion of the Investigator it is necessary for the safety of the patient. If a patient's psychiatric condition can be adequately treated with psychotherapy and/or pharmacotherapy, then the patient, at the discretion of the MHP, may be continued in the trial.

In patients with cognitive impairment or pediatric patients, the ability to complete the C-SSRS or PHQ-9 may be limited. If in the clinical opinion of the Investigator a specific patient cannot complete the instrument(s), the following strategies may be employed:

- Site staff may administer the questions directly to the patient or may ask for the information from a third party, such as a caregiver or family members, as appropriate.
- The Investigator may use his/her clinical judgment to skip any questionnaires that he/she feels are not appropriate for a specific patient.

Any deviation from the intended use of an instrument should be documented by the Investigator, along with the reason for the deviation. If the PHQ-9 and C-SSRS are not administered, the Investigator should document that the issues of depression and suicidality were assessed clinically (e.g., discussion with caregivers).

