8.9.9.1. Columbia-Suicide Severity Rating Scale (C-SSRS)

Patients ≥ 6 years of age

As required in the US by the Food and Drug Administration (FDA), for clinical trials of CNS-acting medications, changes in suicidality as assessed by the C-SSRS will be monitored over the course of the trial to ensure patient safety.

The C-SSRS is a tool used not only to predict suicide attempts but to assess the full range of evidence-based ideation and behavior items, with criteria for next steps (e.g., referral to a MPH). There are 2 versions of the C-SSRS that will be administered according to the SoA (Table 1 and Table 2):

- The Baseline/Screening version of the scale is the initial form of the instrument to assess suicidality in a patient's lifetime. This version can assess a patient's lifetime suicidality for data collection purposes as well as eligibility based on inclusion/exclusion criteria.

- The Since Last Visit version of the scale assesses suicidality since the patient's last visit. This version is meant to assess patients who have completed at least 1 initial C-SSRS assessment and should be used in subsequent visits. The 'Since Last Visit' version of the C-SSRS is asking about any suicidal thoughts or behaviors the patient/participant may have had since the last time the C-SSRS was administered.

To be eligible for the trial, a patient cannot have a suicidal ideation of type 4 or 5, a suicide attempt during the patient's lifetime, or any suicidal behavior in the last month.

Any patient with a suicidal behavior or a suicidal ideation of type 4 or 5 on the CSSRS will be referred to a mental health professional.

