In general, unless otherwise specified, events or measurements happen before the randomization date are in Stage 1 and happen on or after the randomization date are in Stage 2. For patients who are not randomized, all events or measurements are in Stage 1. All events happening after visit 14 will not be considered as in Stage 2 for patients who enrolled into bridging visit unless otherwise specified.

D. Definition of Baseline

Baseline Definition

Baseline will be defined as the last non-missing measurement taken prior to the start of stage 1 open-label treatment administration. In the case where the last non-missing measurement and the reference start date coincide and time of measurement is not available, that measurement will be considered Baseline unless the assessment was scheduled to be post-study drug administration in the SOA. Change from baseline is defined as the post-baseline value minus the baseline value, unless specified otherwise. Percent change from baseline = $(\text{Change from Baseline}/\text{Baseline}) \times 100$.

Study Day

Study Day will be calculated from the reference start date within stage and will be used to show start/stop day of assessments and events. Reference start date is defined as the day of first dose (Day 1) in stage1.

Study Day will be computed as follows:

(Confidential)

- Study Day = (date of event - date of first dose in stage 1) + 1 if the date of the event is on or after the date of first dose.
- Study Day = (date of event - date of first dose in stage 1) if the date of the event is prior to the date of first dose.

E. Missing Data

Unless stated otherwise, missing data will not be replaced with imputed values. When relevant, sections below will address how missing data will be handled for the particular analyses.

Analysis Window

All measurements recorded at unscheduled or early termination visits will be mapped according to the windowed visits by actual study day. These records then will be used for analysis if the scheduled ones are missing. If more than one visit occurs within a single visit window, then the analysis will take the one closest to and before the target day. All scheduled assessments will be analyzed according to the protocol defined visits, regardless of the study day

Stage	Study Visit	Study Week	Study Day	Study Day Window
1	Enrollment Visit	1	1	1
1	Virtual Visit 2	2	14	Post-dose - 21
1	Virtual Visit 3	4	28	22 - 35
1	Virtual Visit 4	6	42	36 - 49
1	Visit 5	8	56	50 - 70

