1. The Baseline/Screening version of the scale is the initial form of the instrument to assess suicidality in a patient's lifetime. This version can assess a patient's lifetime suicidality for data collection purposes as well as eligibility based on inclusion/exclusion criteria.
2. The 'Since Last Visit' version of the scale assesses suicidality since the patient's last visit. This version is meant to assess patients who have completed at least 1 initial C-SSRS assessment and should be used in subsequent visits. The 'Since Last Visit' version of the C-SSRS is inquiries about any suicidal thoughts or behaviors the patient/participant may have had since the last time the C-SSRS was administered.

A frequency and percentage table and a shift from baseline by visit will be provided to display the number of patients who have answered at least one 'Yes' to: Suicidal Ideation (1-5),

Suicidal behavior (6-10), either have suicidal ideation or suicidal behavior (1-10), and the question “Non-Suicidal Self-Injurious Behavior”.

In details, the Suicidal Ideation and Suicidal behavior will include questions as below:

Suicidal Ideation (1-5)

1. Wish to be dead
2. Non-Specific thoughts
3. Ideation without intent to act
4. Ideation with some intent to act
5. Ideation with specific plan

Suicidal behavior (6-10)

6. Preparatory acts or behavior
7. Aborted attempt
8. Interrupted attempt
9. Actual attempt
10. Completed suicide

All C-SSRS data will be listed.

N. Patient Health Questionnaire-9 (PHQ-9)

The PHQ-9 is a 9-item depression scale of the Patient Health Questionnaire and will be used for patients ≥ 12 years of age. After the patient has completed the PHQ-9 questionnaire, it is scored by the trial staff. Any patient with a PHQ-9 score ≥ 10 will be referred to a mental health professional (MHP). The PHQ-9 will be administered according to the SOA.

Summary statistics for the score of summation of the 9 items and changes from baseline will be provided. Frequency count and percentage of number of patients with score ≥ 10 will also be included. Only scores with all 9 items answered will be summarized.

All PHQ-9 data will be listed.

O. Children’s Depression Inventory-2 (CDI-2)

The CDI-2 has both a self-report and a parent version.

The CDI-2: Self-Report Short version is an efficient screening measure that contains 12 items and will be administered to patients < 12 years of age according to the SoA.

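### SAP IX.M counts C-SSRS ideation only as any Yes on items 1–5, so no C-SSRS table separates type 4 or 5, the ideation level at which the protocol excludes and refers patients

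*SAP*

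**What the plan says.** SAP IX.M specifies the C-SSRS output in one sentence. It opens with the planned displays: "A frequency and percentage table and a shift from baseline by visit will be provided". The rest of the sentence sets their content, and the first category is a single composite for ideation, since the displays are meant to "display the number of patients who have answered at least one 'Yes' to: Suicidal Ideation (1-5"). The same at-least-one-Yes rule applies to behavior (items 6–10), to either (items 1–10), and to the single question on non-suicidal self-injury. The ten items are then listed under the words "In details, the Suicidal Ideation and Suicidal behavior will include questions as below". That list defines what goes into each composite; it does not ask for a row per ideation type or per maximum type. All C-SSRS data are also listed by patient.

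The protocol uses a finer threshold. Exclusion criterion 5 (section 6.2) bars "any suicidal ideation of type 4 or 5 on the Columbia-Suicide Severity Rating Scale (C-SSRS) during Screening", along with any lifetime attempt and recent suicidal behavior. During the trial, section 8.9.9 calls for referral to a mental health professional on "Any suicidal ideation of type 4 or 5 on the C-SSRS" or any suicidal behavior. Footnote 16 of the Stage 1 schedule repeats this: "If at any time during the trial a patient has a suicidal ideation of type 4 or 5, or any suicidal behavior". Ideation of types 1–3 neither excludes a patient nor triggers this referral by itself, although the Investigator may refer on judgment.

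On baseline, SAP V.D says: "Baseline will be defined as the last non-missing measurement taken prior to the start of stage 1 open-label treatment administration". IX.M adds nothing specific to the C-SSRS.

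**The concern.** Protocol 8.9.9.1 gives the purpose of the instrument: "changes in suicidality as assessed by the C-SSRS will be monitored over the course of the trial to ensure patient safety". The reason stated in 8.9.9 is that the drug is considered to act through the central nervous system. The ideation items run from a wish to be dead (1) to ideation with a specific plan (5), and the protocol draws its line between 3 and 4. The planned summary draws its only line between none and 1.

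Two things are lost. Escalation across the protocol's line in a patient already positive at baseline shows as no change. The number of patients who reached type 4 or 5 appears in no C-SSRS table, by stage or by arm.

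The SAP does better for comparable data. IX.N counts patients at the PHQ-9 referral score of 10 or more, the adverse event section tabulates by maximum CTCAE grade, and IX.I counts skin findings by most severe outcome.

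**Working it through.** The documents give no figure on this point, so the check applies the SAP's rule to every possible change in ideation.

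**Inputs**
- Level at each assessment: the highest ideation item answered Yes, from 0 (none) to 5 (item list in SAP IX.M). I take the item number as the severity order.
- SAP category: No if the level is 0, Yes if it is 1–5.
- Baseline levels: 0–3. Types 4–5 are excluded at Screening, and eligibility is reconfirmed at the Enrollment Visit (protocol 5.1.2).
- Protocol action level for ideation: 4 or 5.

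**Count of possible worsenings.** From baseline level b there are 5 − b higher levels.

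| Baseline | Worsenings | SAP cell | Of these, reaching 4 or 5 |
|---|---|---|---|
| 0 | 5 | No to Yes | 2 |
| 1 | 4 | Yes to Yes | 2 |
| 2 | 3 | Yes to Yes | 2 |
| 3 | 2 | Yes to Yes | 2 |
| Total | 14 | 9 in Yes to Yes | 8, of which 6 in Yes to Yes |

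- All worsenings: 5 + 4 + 3 + 2 = 14; in Yes-to-Yes: 4 + 3 + 2 = 9.
- Worsenings to type 4 or 5: 4 × 2 = 8; in Yes-to-Yes: 3 × 2 = 6.
- The other 2 (none to 4, none to 5) share the No-to-Yes cell with none to 1, 2 or 3.

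The either (1–10) row is also Yes-to-Yes for these 6. Only new behavior would show, on the behavior row. The frequency table has the same gap, because type 1 and type 5 each count as one Yes.

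**Who is in the baseline Yes group.** Table 1 schedules the C-SSRS at Screening (Day −56 to −14) and at the Enrollment Visit (Day 1). Footnote 16 says the Since Last Visit form is used after Screening. The V.D rule therefore makes the Enrollment Visit form the baseline, and it covers only the interval since Screening, roughly 2 to 8 weeks. A patient whose ideation lies wholly before Screening is a baseline No, so a later type 4 or 5 does appear as a shift, though not as a type 4 or 5. If the lifetime Screening form were used instead, more patients could be baseline Yes and the gap would widen.

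**After regrouping as none / 1–3 / 4–5.** Of the 8 worsenings to type 4 or 5, 0 stay in the same cell. Of all 14, 3 still do (1 to 2, 1 to 3, 2 to 3), all below the action level.

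**The case against.** The strongest reply is that this is a display choice in a descriptive trial. No statistical testing is planned, Stage 2 has about 100 patients, and every item response is listed, so any type 4 or 5 can be found. The affected group is also narrow: ideation in the weeks between Screening and Day 1, in a population screened for unstable psychiatric disorder, any lifetime attempt and PHQ-9 of 15 or more. The behavior half of the action level is tabulated already. Suicidal ideation may also be reported as an adverse event, and treatment-emergent events are tabulated by stage and treatment group and by maximum grade.

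Most of this stands and sets the size of the point. It does not remove it. A listing gives no count by stage or arm, and it is long: 8 scheduled assessments through Week 16 for up to 200 patients and 8 more for about 100 is 8 × 200 + 8 × 100 = 2,400 at full enrollment, before early termination and bridging visits. The adverse event tables are partial cover, because neither document states that a C-SSRS type 4 or 5 must be recorded as an adverse event.

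Three stronger readings are tempting, and the documents do not support them:
- That patients at risk would be missed. Referral is triggered by the response at the visit, not by these tables.
- That the Data Safety Monitoring Board would see only the yes/no summary. SAP V.I lists C-SSRS data for the board without a format, and the board works under a separate charter.
- That Stage 2 would have no other randomized information on suicidality. The adverse event tables by treatment group may carry some.

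**Conclusion.** The point holds for the C-SSRS summary tables. As specified, they cannot show how many patients reached ideation type 4 or 5, and they place 6 of the 8 possible worsenings to that level in the same cell as no change. This rests on three assumptions: IX.M is applied as worded, item number is read as severity, and baselines are limited to none or types 1–3. The counts describe what the table can and cannot distinguish. The documents give no rate of ideation from which to project patients, so how often information would be lost is unknown and may be small. The consequence is for safety reporting only; patient management is unaffected. It is a cheap improvement.

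**What to change.** Keep the current IX.M tables and add two items:

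- (a) A shift table of the most severe category (none / ideation 1–3 / ideation 4–5 / any behavior), from baseline to the worst post-baseline value, by stage and by arm in Stage 2. State which C-SSRS form and which visit is the baseline in each stage; V.D defines only a pre-Stage 1 baseline, and IX.M does not say whether Stage 2 uses it.
- (b) The number and percentage of patients with any post-baseline type 4 or 5 or any suicidal behavior, and how many of these were not at that level at baseline, by stage and by arm in Stage 2.

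The cost is SAP wording and one or two table shells. The item-level data are already collected and listed, and no threshold or procedure changes.

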8.9.9.2. Patient Health Questionnaire -9 (PHQ-9)

The PHQ-9 is a 9-item depression scale of the Patient Health Questionnaire. The PHQ-9 is a tool for assisting clinicians in diagnosing depression as well as selecting and monitoring treatment. After the patient has completed the PHQ-9 questionnaire, it is scored by the trial staff. The PHQ-9 will be administered in patients ≥ 12 years of age or according to the SoA (Table 1 and Table 2).

Any patient with a PHQ-9 score ≥ 10 will be referred to a mental health professional.

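### The SAP's count of patients with PHQ-9 of 10 or more mixes patients already at that level at entry with patients who newly reach it; a by-visit shift table would separate them

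*SAP*

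**What the plan says.** **Entry.** Protocol section 6.2, exclusion criterion 5, excludes a "Patient Health Questionnaire-9 (PHQ-9) score of ≥ 15 during Screening process". Lower scores do not exclude a patient under that part of the criterion.

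**PHQ-9 outputs.** SAP IX.N plans two summaries and a listing of all PHQ-9 data. The continuous summary reads "Summary statistics for the score of summation of the 9 items and changes from baseline will be provided". The categorical one is a "Frequency count and percentage of number of patients with score" of 10 or more. No baseline condition, shift table or second cut-off is stated. This section is not redacted.

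**Referral.** Protocol section 8.9.9.2 uses the same cut-off: "Any patient with a PHQ-9 score ≥ 10 will be referred to a mental health professional".

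**Comparable outputs.** For the C-SSRS, in the section just before, the SAP says "A frequency and percentage table and a shift from baseline by visit will be provided". It also plans shift tables within stage for laboratory data.

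**Baseline.** SAP V.D gives one general definition: "Baseline will be defined as the last non-missing measurement taken prior to the start of stage 1 open-label treatment administration". The laboratory and vital-sign sections refer to change from baseline within stage. IX.N does not say which baseline applies in Stage 2.

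**The concern.** The entry range and the counted range overlap. A patient who enters at 12 and stays at 12 adds one to the count, exactly as does a patient who goes from 2 to 12. A patient who improves from 12 to 8 cancels one who worsens from 8 to 12.

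This matters most in Stage 1, which is open-label and uncontrolled, so each patient's own baseline is the only reference. The protocol monitors depression because the drug is considered to act through the central nervous system (section 8.9.9). A reader of the Stage 1 table would want to know how many patients moved to 10 or above, how many moved below it, and how many reached 15. The planned outputs give none of these numbers directly.

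**Working it through.** The plan states no expected rate for this output, so there is no figure to reproduce. The check has three steps.

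**1. Overlap (from the documents).** Scores allowed by the PHQ-9 part of exclusion 5 are 0 to 14, which is 15 values. Scores counted in IX.N are 10 and above. The overlap is 10, 11, 12, 13 and 14: 5 of the 15 allowed values.

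**2. Carried-in and new cases (assumed shares).** Let N be the number of patients, b the share entering at 10 to 14 and not changing, and i the share of the others who reach 10 or more.

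- Planned count = N·b + N·(1 − b)·i
- New cases = N·(1 − b)·i, out of N·(1 − b)

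N = 200 is the protocol's upper limit for Stage 1 and overstates the PHQ-9 population. The values of b and i are assumptions.

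| b | i | Planned count | New cases | Carried-in share of count |
|---|---|---|---|---|
| 5% | 0% | 10.0 (5.0%) | 0 of 190 | 100% |
| 5% | 2% | 13.8 (6.9%) | 3.8 of 190 | 72% |
| 5% | 5% | 19.5 (9.8%) | 9.5 of 190 | 51% |
| 10% | 0% | 20.0 (10.0%) | 0 of 180 | 100% |
| 10% | 2% | 23.6 (11.8%) | 3.6 of 180 | 85% |
| 10% | 5% | 29.0 (14.5%) | 9.0 of 180 | 69% |
| 20% | 0% | 40.0 (20.0%) | 0 of 160 | 100% |
| 20% | 2% | 43.2 (21.6%) | 3.2 of 160 | 93% |
| 20% | 5% | 48.0 (24.0%) | 8.0 of 160 | 83% |

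In Stage 2, randomization balances carried-in scores in expectation but dilutes the contrast. With assumed new-case rates of 10% and 5% (ratio 2.0) and b = 10%, the ratio of planned counts is (0.10 + 0.90 × 0.10) / (0.10 + 0.90 × 0.05) = 0.190 / 0.145 = 1.31. For b = 5% it is 1.49 and for b = 20% it is 1.17.

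**3. Movement hidden by a stable count, and the choice of shift (simulation, no drug effect).** The true score is normal, clipped to 0–27. Each observed score is the true score plus visit noise, rounded. Entry requires a screening score below 15, followed by Day 1 and six Stage 1 visits with no drift. Means, SDs and noise are assumptions.

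- New at Week 16 among Day 1 below 10 = P × (1 − s) / (1 − D). P is the share at 10 or more at Week 16, s the share of those already at 10 or more on Day 1, and D the share at 10 or more on Day 1 (equal to P within 0.1 point).
- For mean 6, SD 4.5, noise 1.5: 20.1% × 0.28 / 79.9% = 7%.

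| Mean / SD / noise | P | s | New at Week 16 | At 10 or more at any of six visits, Day 1 below 10 |
|---|---|---|---|---|
| 4 / 4 / 1.5 | 9.2% | 63% | 4% | 11% |
| 4 / 4 / 2.5 | 11.3% | 47% | 7% | 21% |
| 6 / 4.5 / 1.5 | 20.1% | 72% | 7% | 19% |
| 6 / 4.5 / 2.5 | 21.4% | 58% | 11% | 32% |
| 8 / 4.5 / 1.5 | 31.8% | 77% | 11% | 27% |
| 8 / 4.5 / 2.5 | 32.3% | 65% | 17% | 43% |

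Two results follow. The net count is flat from Day 1 to Week 16 although 23% to 53% (that is, 1 − s) of those counted at Week 16 were below 10 on Day 1; an equal number moved the other way. And taking the worst of six visits produces 11% to 43% apparent new cases with no drug effect, more than the planned Week 16 count in four of the six scenarios.

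**The case against.** The strongest reply is that the count does what it is for. It follows the referral rule in IX.N and uses the same cut-off, so a patient who stays at 12 belongs in it. The SAP does not call it a depression rate or an incidence, and it plans no statistical testing. This stands, and is the reason to keep the count.

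A reader might go further and infer that the planned tables conceal real worsening, or that a score of 15 or more would go unseen. The documents do not support that. The default continuous statistics in SAP V.N include the maximum. A rise from 11 to 20 makes the maximum score at least 20 and the maximum change at least +9, and any score of 15 or more shows in the maximum score. All PHQ-9 data are listed, the DSMB receives unblinded PHQ-9 and C-SSRS data, and worsening of a pre-existing condition falls under the adverse event definition. What remains missing is the number of patients who moved.

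A reader might also infer that the Stage 1 percentage must mislead. In the simulation, Day 1 and Week 16 prevalence agree, so a reader who compared the two would correctly see no net change. But two marginal percentages give only the net difference. The simulated carry-over is also partly true by construction, since no drug effect was modelled, and the model leaves out exclusion 4 on unstable psychiatric disorders.

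Finally, replacing the count with a worst-value headline of new cases would be worse in one respect: with no drug effect it gives the inflated rates shown above.

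**Conclusion.** The point holds in a limited form. The count at 10 or more includes a range allowed at entry and is not conditioned on baseline, so it cannot separate patients already at that level from patients who newly reach it. The group-level change summary does not fill the gap. This follows from the text alone.

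The size is not established, because the documents do not give the entry distribution. Under the assumed shares, carried-in patients make up 51% to 100% of the planned count; under the assumed simulation scenarios, 47% to 77% of the Week 16 count. These ranges illustrate the problem and are not estimates for this trial.

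This is an inexpensive improvement to a descriptive safety table. It does not bear on the entry threshold or the referral threshold.

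**What to change.** In SAP IX.N:

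- Keep the count at 10 or more, labelled as the number meeting the referral criterion.
- Add a shift from baseline by visit, as planned for the C-SSRS, with categories below 10, 10 to 14, and 15 or more. Present it by stage, and by treatment in Stage 2.
- Use as denominator the patients with both a baseline and a post-baseline PHQ-9. The default in SAP V.N is the whole analysis population, which includes patients under 12 who do not receive the PHQ-9.
- State which baseline applies in Stage 2: the value before the first open-label dose, or the Stage 2 entry value.
- If a worst post-baseline version is produced, make it supplementary and do not label it as the headline rate of new cases.

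The cost is a short addition to the SAP and one table in a layout it already uses. No new data, visits or protocol changes are needed. One limitation remains: some by-visit crossings will reflect measurement noise and regression to the mean (4% to 17% of patients below 10 on Day 1 are at 10 or more at Week 16 in the simulation), so the Stage 1 shifts still need cautious reading.
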